**CONFIDENTIAL PROTOCOL**

An Open Label, Safety Study to Assess the Potential for Adrenal Suppression Following Treatment with Desoximetasone 0.15% Topical Spray (Taro Pharmaceuticals U.S.A., Inc.) in Patients with Atopic Dermatitis

Basal (pre Cortrosyn™ injection)	≥ 5 mcg/100ml	< 5 mcg/100ml
30 minutes post Cortrosyn™ injection	≥ basal value + 7	< basal value + 7
	> 18 mcg/100ml	≤ 18 mcg/100ml

HPA Axis suppression will be defined as a 30 minute post Cortrosyn™ injection level cortisol level of ≤ 18 mcg/100ml. As the study treatment period will be over, any patients with results of HPA axis suppression will be advised not to initiate any new steroid therapy, topical or otherwise, and to return to the site in 28 days at which time they will be assessed for HPA axis suppression.

Any patient presenting with symptoms of HPA axis suppression, such as nausea, headache, myalgia, fatigue or loose stool, will be referred to an endocrinologist. As an additional safety precaution, wristbands identifying the patient as someone suffering from adrenal suppression secondary to steroid withdrawal will be provided to alert medical personnel should any emergencies arise before adrenal function returns to normal.

If the results of the cortisol response test still show signs of HPA axis suppression 28 days after discontinuing therapy the patient will be asked to return in 28 days (56 days after discontinuing steroid therapy) for another follow-up test. If the patient is still showing signs of HPA axis suppression 56 days after discontinuing steroid therapy and presents with related symptoms the patient will be referred to an endocrinologist.

If HPA axis suppression persists for 56 days after discontinuing steroid therapy, but the patient has no symptoms they will be asked to return in 28 days (84 days after discontinuing steroid therapy) for another follow-up test. If HPA axis suppression persists for 84 days after discontinuing steroid therapy the patient will be referred to an endocrinologist regardless of symptoms.

Patients should not be subjected to Cortrosyn™ testing, or any other challenge to their adrenal response, any sooner than 4 weeks from their last Cortrosyn™ test.

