**CONFIDENTIAL PROTOCOL**

An Open Label, Safety Study to Assess the Potential for Adrenal Suppression Following Treatment with Desoximetasone 0.15% Topical Spray (Taro Pharmaceuticals U.S.A., Inc.) in Patients with Atopic Dermatitis

HPA Axis Evaluation	
Prior to the first dose of study drug and at the end of the study (Day 28 or early termination) all patients will have a cortisol response test performed using the procedure of Wood et al. (See Appendix E). Only those patients with normal adrenal function at baseline will be enrolled and dispensed study drug. If at the end of the study the patient has a cortisol response test that is suggestive of HPA axis suppression, they will have a follow test at least every 4 weeks until such time as the Investigator considers the adrenal function has turned to normal.
 
Cohorts will be enrolled in sequential order. Each cohort will initiate enrollment once the previous cohort has reached the minimum number of patients and a safety analysis has been reviewed. Each cohort will be enrolled based on the availability of patients.
 
Each cohort will be reviewed for the potential of HPA axis suppression. If at least 50% of patients in each Cohort experience HPA axis suppression, enrollment for that cohort will be stopped and no further cohorts will be initiated. If at least 35% of patients have experienced HPA axis suppression across cohorts combined during the study, enrollment will be discontinued and no other cohorts will be initiated. Cohort 2 will not begin until safety data has been reviewed for Cohort 1. The same process will be followed for each Cohort until the study is complete.
 
Primary Analysis:
 
Proportion of patients in the study with HPA axis suppression following treatment with the study medication.
 
Secondary Analysis:
 
A logistic regression of the proportion of patients in the study with HPA axis suppression will be performed with % BSA affected as a covariate.

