## **CONFIDENTIAL PROTOCOL**

An Open Label, Safety Study to Assess the Potential for Adrenal Suppression Following Treatment with Desoximetasone 0.15% Topical Spray (Taro Pharmaceuticals U.S.A., Inc.) in Patients with Atopic Dermatitis

---

- Signs and symptoms of possible HPA axis suppression
- Protocol deviations/violations that in the Investigator's opinion warrant discontinuation

Non-compliance with dosing need not be a reason for early termination. Patients who withdraw or are removed from the study will not be replaced. In the event a patient withdraws or is dropped from the study for any reason, the Investigator will request return of the unused product and report the reason for the discontinued participation.

When a patient discontinues early from the study, all study procedures required for the end of study should be performed at their last study visit. Patients who are discontinued from the study after enrollment will be evaluated for safety and will be given, or referred for, appropriate treatment.

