#### 9.5.1 Visit 1 (Day 1): Screening/Enrollment, Before 12 pm

1. **Informed Consent:** For patients under the age of majority in the state the study is being conducted (18 years in most states) the parent or legal guardian should sign the consent form and the child (age  $\geq$  11 years old) will be required to sign a patient "assent" form that will be written in such a way as to be understandable to a child. Patients age 6-10 years of age will provide verbal assent to participate.
2. **Medical History and Demographics:** The patient's demographic and a complete medical history will be obtained for the patient's current and past medical conditions.
3. **Physical Examination and % BSA Assessment:** A general physical exam will be conducted. The patient's body weight (kg) and height (cm) will also be measured while the patient is lightly clothed (e.g., no coat or shoes). %BSA will be assessed using instructions in Appendix A.
4. **Vital Signs:** The patient's vital signs will be taken and recorded (pulse, blood pressure, temperature and respiration rate).
5. **Pregnancy Test:** A urine pregnancy test will be required of all females of child bearing potential prior to enrollment.
6. **Dermatological Assessment:** Clinical signs and symptoms of AD will be evaluated by the Investigator based on the following:
  - EASI Score (Appendix B)
  - IGA Score (Appendix C)
  - Application Site Reactions (Appendix D)
7. **Concomitant Medication:** Review with the patient and parent/legal guardian the patient's use of concomitant medication within the last 12 weeks.
8. **Confirm Inclusion/Exclusion Met:** Confirm the patient meets all inclusion/exclusion criteria pending results of the Cortisol Response Test.

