## CONFIDENTIAL PROTOCOL

An Open Label, Safety Study to Assess the Potential for Adrenal Suppression Following Treatment with Desoximetasone 0.15% Topical Spray (Taro Pharmaceuticals U.S.A., Inc.) in Patients with Atopic Dermatitis

---

9. **Laboratory Evaluations:** A blood sample will be collected for hematology and clinical chemistry testing. (See Appendix G).
10. **Cortisol Response Test:** All patients will have a cortisol response test performed according to the procedure detailed in Appendix E.
11. **Dispense Study drug:** If patient is eligible to enroll, record the weight of one bottle of study drug and dispense with instructions.
12. **Apply Study Medication:** The first dose of study medication should be administered by the patient ( $\geq 12$  years of age) or parent/legal guardian at the site, under staff supervision.
13. **Provide Dosing Diary:** Provide Diary and instruct parent/legal guardian regarding how it is to be filled out and how study drug is to be used.
14. **Dispense Sunscreen:** For use only when sun exposure cannot be avoided.
15. **Provide Patient Wristband:** Each patient will receive a wristband to indicate that the patient is using a medication that has the potential to cause HPA axis suppression.
16. Schedule Visit 2.

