### 9.5.3 Visit 3 (Day 29±2): End of Study or Early Termination, Before 12 pm

1. **Vital Signs:** The patient's vital signs will be recorded (pulse, blood pressure, temperature and respiration rate).
2. **Pregnancy Test:** A pregnancy test will be required of all females of child bearing potential prior to enrollment.
3. **Physical Exam:** A general physical exam will be conducted.
4. **% BSA Assessment:** % BSA covered with atopic dermatitis will be assessed using instructions in Appendix A.
5. **Dermatological Assessment:** Clinical signs and symptoms of AD will be evaluated by the Investigator based on the following:
  - EASI Score (Appendix B)
  - IGA Score (Appendix C)
  - Application Site Reactions (Appendix D)
6. **Concomitant Medication:** Review with the patient and parent/legal guardian the patient's use of new or change in ongoing concomitant medication since Visit 2.
7. **Adverse Events:** Patients will be questioned about any health status changes/adverse events since last visit. All events will be recorded.
8. **Evaluation of Patient Compliance to the Protocol:** Collect and review patient's dosing diary for compliance. Non-compliance with dosing does not warrant dismissal from the study.
9. **Collect Study Drug:** The used bottle of study drug will be collected and the weight recorded.
10. **Laboratory Evaluations:** A blood sample will be collected for hematology and clinical chemistry testing. (See Appendix G).
11. **Cortisol Response Test:** All patients will have a cortisol response test performed according to the procedure detailed in Appendix E.

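### As worded, the 4-week bar on repeat Cortrosyn testing conflicts with a Visit 3 on Day 27 or 28 and with every early-termination test before Day 29

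*Protocol*

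**What the plan says.** Protocol 9.6.15 ends its account of the cortisol response test by barring any Cortrosyn test, or other adrenal challenge, "any sooner than 4 weeks from their last Cortrosyn™ test". Protocol Appendix E and SAP Appendix D repeat the sentence. None of the three exempts Visit 3 or early termination.

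The schedule requires two tests.

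- **Baseline.** Section 9.5.1 is headed "Visit 1 (Day 1): Screening/Enrollment, Before 12 pm" and instructs: "All patients will have a cortisol response test performed according to the procedure detailed in Appendix E".
- **End of treatment.** Section 9.5.3 is headed "Visit 3 (Day 29±2): End of Study or Early Termination, Before 12 pm" and repeats the test instruction. The synopsis, under HPA Axis Evaluation, says "at the end of the study (Day 28 or early termination) all patients will have a cortisol response test performed". The title of SAP table T16.1.9.5 also refers to Day 28.

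For a patient who stops early, Protocol 9.3.4 says "all study procedures required for the end of study should be performed at their last study visit", which includes the cortisol test. One of its listed reasons for early termination is "Signs and symptoms of possible HPA axis suppression". It adds: "Patients who withdraw or are removed from the study will not be replaced".

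The primary analysis (Protocol 10.1.3, SAP 7.2) needs both a post-treatment cortisol test and at least 42 doses. SAP 7.5 gives no rule for a missing post-treatment cortisol result.

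**The concern.** A site holding these documents has two instructions for the same patient: do the test at the early last visit, and do no test within 4 weeks of Day 1. Before Day 29 both cannot be followed.

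If the site follows 9.3.4 and the synopsis, the endpoint exists but the bar is breached. If it follows the bar, there is no post-treatment result and the patient leaves both the numerator and the denominator of the primary proportion. Suspected HPA suppression is itself a reason to withdraw, so the missing result could be related to the outcome being measured. Cohort minimums are 10 (Cohort 1) and 5 (Cohorts 2 to 4), and withdrawn patients are not replaced, so one patient visibly moves a cohort's rate.

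**Working it through.** **Inputs.** The bar is 4 weeks = 28 days (Protocol 9.6.15). Baseline test on Day 1 (9.5.1). Visit 3 on Day 29 ± 2, so Days 27 to 31 (9.5.3). Dosing twice daily from Day 1 and none within 12 hours of the test visit (9.4.1). Dose rule of 42 (10.1.3).

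**Nominal schedule.** Elapsed days = visit day − 1. For Day 29 this is 29 − 1 = 28 days, exactly 4 weeks. The nominal schedule meets the bar with no slack.

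**Visit 3 window.**

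| Visit 3 day | Days since baseline test | Meets the bar? |
|---|---|---|
| 27 | 26 | No |
| 28 | 27 | No |
| 29 | 28 | Yes |
| 30 | 29 | Yes |
| 31 | 30 | Yes |

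Two of the five permitted days conflict. The synopsis's Day 28 test is 27 days after baseline and also conflicts.

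**Early termination.** Any test before Day 29 is at most 28 − 1 = 27 days after baseline, so all of them conflict with the wording.

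**When the bar alone removes the endpoint.** With full dosing and none on the day of the visit, doses by a visit on Day d = 2 × (d − 1).

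- Day 21 or earlier: at most 2 × 20 = 40 doses. The 42-dose rule already excludes the patient, tested or not.
- Day 22: 2 × 21 = 42 doses, so the dose rule is met.
- Day 28: 2 × 27 = 54 doses, so the dose rule is met.

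For a fully dosed patient the bar is therefore decisive only for termination visits on about Days 22 to 28.

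**Effect on a reported rate (illustration).** Assume one untested child was truly suppressed and leaves the denominator. With 4 suppressed of 10, the rate is 4/10 = 40%. Without that child it is reported as 3/9 = 33.3%.

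**Direction of the proposed row.** Adding k untested withdrawals as suppressed changes x/n to (x + k)/(n + k), which is never below x/n. With x = 3, n = 9 and k = 1 it gives 4/10 = 40%.

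**The case against.** The best answer is placement. In all three locations the sentence closes the paragraphs on follow-up of abnormal results and stands directly above the follow-up schedule. The early-termination test is separately and specifically required. A site could reasonably take the bar to govern repeat follow-up tests only, and then every termination test is done and nothing is lost. That reading is plausible and may be what was intended. But the wording reaches back to the patient's last Cortrosyn test, whichever that was, and 9.6.15 carries it under the Visit 3 Test heading. Nothing in the text settles the matter.

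Several stronger conclusions are tempting, and the documents do not support them.

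- A reader might infer that every patient terminating before Day 29 loses the primary endpoint because of the bar. The conflict of wording is that wide. The loss is not, because the 42-dose rule already removes fully dosed patients who stop by about Day 21.
- A reader might infer that completers lose their endpoint. They need not: Days 29 to 31 satisfy both passages.
- A reader might set 3/9 against the 35% combined stopping threshold and conclude that the cohort reviews are distorted. The documents do not define the denominator for those reviews or say that untested patients are dropped from them.
- A reader might state that the observed rate is biased downward. That requires a site to put the bar above 9.3.4 and the untested child to be truly suppressed. The symptoms named in 9.6.15, such as headache, nausea and fatigue, are non-specific.

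It is also fair that missing tests would be visible. L16.2.1 lists discontinuation reasons, L16.2.3 lists exclusions from the HPA analysis, and L16.2.6.1 records whether a test was done. Listings show the gap, but they do not say how it counts in the reported proportion.

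**Conclusion.** The point stands as an internal inconsistency with a limited but real route to the primary endpoint. As worded, the bar conflicts with two of the five Visit 3 days, with the synopsis's Day 28 test and with all early-termination tests before Day 29.

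The possible loss of a primary result attributable to the bar alone is confined to terminations on about Days 22 to 28. This assumes full twice-daily dosing and the 42-dose rule. Protocol 9.4.6 instead speaks of 75% to 125% of scheduled doses; if that means doses scheduled up to discontinuation, the span would be wider.

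Whether any result is lost depends on which passage a site follows. Whether a loss lowers the rate depends on the true status of the untested child. The fall from 40% to 33.3% is an illustration under those assumptions, not a forecast.

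**What to change.** **Protocol and SAP wording.** Reconcile the synopsis, Protocol 9.3.4, 9.5.3, 9.6.15 and Appendix E, and SAP Appendix D, so that it is clear whether the 4-week interval applies to the Visit 3 and early-termination tests. SAP Appendix D also places the end-of-study test at Visit 4, which the schedule defines as a telephone call, and should be aligned in the same edit. Which rule should prevail, and what the interval should be, are for the sponsor; neither is proposed here.

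**SAP T16.1.9.5.** Add one sensitivity row that counts as suppressed any patient withdrawn for signs or symptoms of HPA suppression who has no post-treatment test. Label it a conservative bound and show how many patients it adds. The withdrawal reason must be identifiable in L16.2.1.

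Leave the primary analysis and the cohort stopping rules as they are. Suppression is defined biochemically, as a 30-minute cortisol of 18 mcg/100 ml or less. Imputing it from symptoms within the cohort reviews would change how the enrolment-stopping rules operate.

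**Cost.** Wording changes and one table row. The row can only leave the reported rate unchanged or make it less favourable.

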**Follow-Up Schedule for Patients showing signs of HPA Axis Suppression**

Days after d/c	HPA Results	Symptoms	Patient Course
28	Normal	N/A	Study over
28	Abnormal	Yes	Refer to endocrinologist
28	Abnormal	No	Repeat test in 28 days
56	Normal	N/A	Study over
56	Abnormal	Yes	Refer to endocrinologist
56	Abnormal	No	Repeat test in 28 days
84	Normal	N/A	Study over
84	Abnormal	Yes or No	Refer to an endocrinologist

**9.7 Adverse Events**

The patients will be monitored throughout the study for any Adverse Events (AE). AEs will be collected through both solicited and unsolicited means and subsequently coded in tabular form using the MedDRA (Version 19 or higher) Adverse Event Dictionary. The patients will be encouraged to report signs, symptoms, and any changes in health to the clinic staff. Severity of each AE will be determined by the staff based on observation and questioning of the patients. The Investigator will

## CONFIDENTIAL PROTOCOL

An Open Label, Safety Study to Assess the Potential for Adrenal Suppression Following Treatment with Desoximetasone 0.15% Topical Spray (Taro Pharmaceuticals U.S.A., Inc.) in Patients with Atopic Dermatitis

---

judge the relationship of the event to the study treatments. Adverse events should be followed up until they have resolved or stabilized.

### 9.7.1 Adverse Event Definitions

Adverse Event: Any untoward medical occurrence in a patient or clinical investigation patient administered a pharmaceutical product and which does not necessarily have a causal relationship with treatment. An AE can therefore be any unfavorable and unintended sign, symptom, or disease, temporally associated with the use of a medicinal (investigational) product, whether or not related to this product. This includes events not seen at baseline, or worsened even if present at baseline.

Unexpected Adverse Event: An adverse event where the nature or severity of is not consistent with the applicable product information (e.g., Investigator's Brochure for an unapproved investigational product or package insert/summary of product characteristics for an approved product).

Adverse Drug Reaction: All noxious and unintended responses to a medical product related to any dose should be considered adverse drug reactions. The response to a 'medical product' means that a causal relationship between a medicinal product and an adverse event is at least a reasonable possibility, i.e., the relationship cannot be ruled out.

### 9.7.2 Severity of Adverse Event

The severity of the adverse event will be graded by the Investigator using the following criteria as guidelines:

- MILD: Awareness of symptom but does not interfere with routine activities.
- MODERATE: Discomfort sufficient to interfere with routine activities.
- SEVERE: Impossible to perform routine activities.

### 9.7.3 Relationship of Adverse Event

#### Relationship to the Study Product

- NOT RELATED: Any AE that is clearly not related to use of the study drug.
- POSSIBLE: The association of the AE with the study drug is unknown; however, a relationship between the drug and event cannot be ruled out.
- PROBABLE: There is reasonable temporal relationship between the use of the study drug and the AE. Based upon the Investigator's clinical experience, the association of the event with the study drug seems likely.
- DEFINITE: The AE occurs following the application of the study drug and it cannot be reasonably explained by any other known characteristics of the patient's clinical state, environmental or toxic factors, or other modes of treatment administered to the patient. It disappears or decreases upon discontinuation of the study medication and reappears on a re-challenge of the study drug.

## **CONFIDENTIAL PROTOCOL**

An Open Label, Safety Study to Assess the Potential for Adrenal Suppression Following Treatment with Desoximetasone 0.15% Topical Spray (Taro Pharmaceuticals U.S.A., Inc.) in Patients with Atopic Dermatitis

---

### **9.7.4 Patient's Participation Stopping Criteria**

In the opinion of the Investigator, if the patient suffers an AE that warrants discontinuation of the study drug due to interference with age-appropriate instrumental ADL (Activities of Daily Living), for example preparing for meal, shopping for groceries or clothing, using the telephone, etc. the patient will be followed until the AE resolves or is considered stable. Any subject that discontinues the study due to an adverse event will be followed until resolution or stabilization of the adverse event.

## **9.8 Serious Adverse Events**

### **9.8.1 Definition of a Serious Adverse Event**

A Serious Adverse Event (SAE) is any untoward medical occurrence that at any dose suggests a medically significant hazard, including any event that:

- Results in death – includes all deaths, even those that appear to be completely unrelated to study treatment (e.g., car accident where patient is a passenger).
- Is life-threatening – in the view of the Investigator, the patient is at immediate risk of death at the time of the event.
- Results in persistent or significant disability or incapacity (substantial disruption of one's ability to conduct normal life).
- Requires inpatient hospitalization or prolongation of existing hospitalization.
- Causes congenital anomaly or birth defect.
- Is an important medical event that may not be immediately life-threatening or result in death or hospitalization, but may jeopardize the patient or may require medical or surgical intervention to prevent one of the serious outcomes listed above (e.g., intensive treatment in an emergency room, convulsions that do not result in hospitalizations). Emergency Room visits that require medical or surgical intervention to prevent one of the other serious outcomes listed above are considered a Serious Adverse Event.

### **9.8.2 Reporting Serious Adverse Events**

#### Investigator Reporting of SAEs

Adverse events which are evaluated by the Investigator as "Serious" will be reported to the Sponsor and IRB within 24 hours of notice whether or not they are considered expected or drug-related. All SAEs will be reported as per applicable regulations. All SAEs encountered during the study will be reported on the appropriate form and summarized in the final report.

**Any serious or unexpected adverse events should be reported to Novum within 24 hours.  
Following is the contact information:**

[name]  
Vice President, Clinical Trials  
[contact]  
[contact] [name]  
[contact]  
Or

